9.2. Analysis of Study Endpoint

This study is intended to provide descriptive and comparative data on the incidence rates of the selected study endpoints in the two study groups.

1. Descriptive statistics (ie, frequency, percent, mean, median, standard deviation as appropriate depending on data type) will be used to summarize baseline characteristics (clinical and demographic) of patients enrolled in the study. (Potential variables include but are not limited to age, gender, weight, BMI, race, smoking, alcohol consumption, HIV-1 RNA level, CD4+ T lymphocyte counts, duration of antiretroviral therapy, duration of HIV infection, number of failed regimens etc).
2. Cumulative incidence rates and incidence-density rates of the study endpoints in the two groups will be reported along with respective 95% confidence intervals.
3. Subject discontinuation, loss to follow-up and total person-time of follow-up accrued in the study will be summarized.
4. Depending on data availability, subgroup analyses may be performed to further describe the rates of the study endpoints stratified by age group, gender, baseline CD4+ cell counts, baseline viral load, hepatitis C/hepatitis B serology, duration of maraviroc use, total duration of antiretroviral use, components of OBT etc.
5. In addition to the selected study endpoints, SAEs and adverse reactions reported during the study will be summarized in summary tables and listings.
6. Crude and adjusted rate ratios with 95% confidence intervals will be calculated for each study endpoint comparing maraviroc-exposed patients to maraviroc-unexposed patients. Multivariate analysis techniques, including recurrent event analyses techniques, will also be used as appropriate to account for the baseline difference in the two study groups and recurrent events if any for a given subject, respectively.

In addition, incidence rates in patients receiving maraviroc in this study may be compared to those reported in comparable patients not using maraviroc in other HIV-1 infected cohort(s) such as EuroSIDA. The baseline characteristics of the patients (eg, number of failed regimens, CD4+ T lymphocyte counts) in this study will be used to identify comparable subjects from the external cohort(s).

10. QUALITY CONTROL AND QUALITY ASSURANCE

During study conduct, Pfizer or Sponsor will conduct periodic monitoring visits of sites at least once a year to ensure that the protocol is being followed. The monitors may review source documents to confirm that the data recorded on questionnaire pages is accurate. The enrolling physician and institution will allow the Sponsor or its designated representatives and appropriate regulatory authorities direct access to source documents to perform this verification.

The study site may be subject to review by the Institutional Review Board (IRB)/Independent Ethics Committee (IEC), and/or to quality assurance audits performed by the Sponsor or its designated representative, and/or to inspection by appropriate regulatory authorities.

It is important that the enrolling physician(s) and their relevant personnel are available during the monitoring visits and possible audits or inspections and that sufficient time is devoted to the process.

11. DATA HANDLING AND RECORD KEEPING

11.1. Questionnaires

As used in this protocol, the term questionnaire refers to either a paper form or an electronic data record or both, depending on the data collection method used in this study.

Baseline (screening and enrollment), follow-up, and final disposition questionnaires are required and should be completed for each included subject. The completed original questionnaires are the sole property of the Sponsor and should not be made available in any form to third parties, except for authorized representatives of the Sponsor or appropriate regulatory authorities, without written permission from the Sponsor.

The enrolling physician has ultimate responsibility for the accuracy and authenticity of all clinical, safety, laboratory data entered on the questionnaires. The questionnaires must be signed by the enrolling physician or by an authorized staff member to attest that the data contained on the questionnaires is true. In most cases, the source documents are the hospital's or the physician's subject chart. In these cases data collected on the questionnaires must match the data in those charts.

In some cases, the questionnaire, or part of the questionnaire, may also serve as source documents. In these cases, a document should be available at the enrolling physician's site as well as at the Sponsor and clearly identify those data that will be recorded in the questionnaire, and for which the questionnaire will stand as the source document.

11.2. Record Retention

To enable evaluations and/or audits from regulatory authorities or the Sponsor, the enrolling physician agrees to keep records, including the identity of all participating subjects (sufficient information to link records, eg, questionnaires and hospital records), all original signed informed consent forms, copies of all questionnaires, serious adverse event forms, source documents, and detailed records of treatment disposition. After the end of the study the records should be retained by the enrolling physician according to local regulations or as specified in the Clinical Study Agreement, whichever is longer.

If the enrolling physician relocates, retires, or for any reason withdraws from the study, Pfizer, as the Sponsor's designee should be prospectively notified. The study records must be transferred to an acceptable designee, such as another enrolling physician, another

090177e1928d33f51Approved Approved On: 07-Jan-2020 12:23 (GMT)

institution, or to Pfizer. The enrolling physician must obtain Pfizer's written permission before disposing of any records, even if retention requirements have been met.

12. ETHICS

12.1. Institutional Review Board (IRB)/Independent Ethics Committee (IEC)

It is the responsibility of the enrolling physician to have prospective approval of the study protocol, protocol amendments, informed consent forms, and other relevant documents, eg, advertisements, if applicable, from the IRB/IEC. All correspondence with the IRB/IEC should be retained in the Enrolling Physician File. Copies of IRB/IEC approvals should be forwarded to Pfizer.

The only circumstance in which an amendment may be initiated prior to IRB/IEC approval is where the change is necessary to eliminate apparent immediate hazards to the subjects. In that event, the enrolling physician must notify the IRB/IEC and the Study Team in writing within 5 working days after the implementation.

12.2. Ethical Conduct of the Study

The study will be conducted in accordance with the International Conference on Harmonization (ICH) guidelines. In addition, the study will be conducted in accordance with the protocol, the International Society for Pharmacoepidemiology's Good Pharmacoepidemiology Practices, and applicable local regulatory requirements and laws.

12.3. Subject Information, Consent and Confidentiality

All personal study subject data collected and processed for the purposes of this study will be managed by the enrolling physician and his/her staff with adequate precautions to ensure the confidentiality of those data, and in accordance with applicable national and/or local laws and regulations on personal data protection.

Only the enrolling physician and his/her designee, authorized agents of Pfizer, Inc., or of a CRO designated by Pfizer Inc. following the guidelines proposed by the ethics committees approving this research, will be granted direct access to the study subjects' original medical and hospital records for verification of study procedures and/or data, without violating the confidentiality of the subjects, to the extent permitted by the law and regulations. The Sponsor will not have access to the study subject's address, phone number, social security number or any other national identification number or alternate contact information collected for the purpose of this study.

All parties will ensure protection of subject personal data and will not include subject names on any sponsor forms, reports, publications, or in any other disclosures. In case of data transfer, Pfizer and Sponsor will maintain high standards of confidentiality and protection of subject personal data.

090177e1928d33f51Approved On: 07-Jan-2020 12:23 (GMT)

Informed consent must take place prior to enrollment of subjects in the study. Written, signed and dated informed consent will be obtained from each subject in accordance with local regulatory and legal requirements.

The informed consent form must be agreed to by the Sponsor or designee and the IRB/IEC and must be in compliance with local regulatory requirements and legal requirements.

The consent document will be available in English and in all applicable local languages depending on the site and country.

The completed and signed consent forms will be stored in a locked file cabinet at the study site. A separate document will include the secondary contact information provided by the subject and, where allowed by law, the social security number or any other national identification number or national insurance number. One copy of this contact form will be stored in a locked file cabinet at the study site. In countries where the CRO is allowed to contact the secondary contact person or the patient, a second copy of this contact form will be stored at the designated CRO office, separate from other data, and in locked file cabinets to insure confidentiality.

The enrolling physician must ensure that each study subject, or his/her legally acceptable representative, is fully informed about the nature and objectives of the study and possible risks associated with participation. The enrolling physician, or a person designated by the enrolling physician, will obtain written informed consent from each subject or the subject's legally acceptable representative before any study-specific activity is performed. The informed consent form used in this study, and any changes made during the course of the study, must be prospectively approved by both the IRB/IEC and the Sponsor before use. The enrolling physician will retain the original of each subject's signed consent form.

If the consent form is revised during the course of the study, it is the enrolling physician's responsibility to ensure that an amended consent receives approval/favorable opinion by the local IRB/IEC, and signed by all patients subsequently participating in the study.

13. SPONSOR DISCONTINUATION CRITERIA

Premature termination of this study may occur because of a regulatory authority decision, change in opinion of the IRB/IEC, drug safety problems, or at the discretion of the Sponsor.

If a study is prematurely terminated or discontinued, the Sponsor or designee will promptly notify the enrolling physician. After notification, the enrolling physician must contact all participating subjects within one month. As directed by Pfizer, all study materials must be collected and all questionnaires completed to the greatest extent possible.

14. COMMUNICATION AND PUBLICATION OF STUDY RESULTS

Publication of study results is discussed in the Clinical Study Agreement.

Communication of Results

Where required by applicable regulatory requirements, an investigator signatory will be identified for the approval of the clinical study report. The investigator will be provided reasonable access to statistical tables, figures, and relevant reports and will have the opportunity to review the complete study results at a Sponsor site or other mutually-agreeable location.

Sponsor will also provide the investigator with the full summary of the study results. The investigator is encouraged to share the summary results with the study subjects, as appropriate.

The results summary will be posted to an internet-based study register at the time of the first regulatory approval or within 12 months of study completion or of any decision to terminate development. In addition, a manuscript will be submitted to a peer-reviewed journal for publication within 12 months of the first regulatory approval or within 12 months of study completion or of any decision to terminate development. When manuscript publication in a peer-reviewed journal is not feasible, further study information will be posted to an internet-based study register to supplement the results summary.

Publications by Investigators

ViiV Healthcare has no objection to publication by Investigator of any information collected or generated by Investigator, whether or not the results are favorable to the Investigational Drug. However, to ensure against inadvertent disclosure of Confidential Information or unprotected Inventions, Investigator will provide ViiV Healthcare and/or designee an opportunity to review any proposed publication or other type of disclosure before it is submitted or otherwise disclosed.

Investigator will provide manuscripts, abstracts, or the full text of any other intended disclosure (poster presentation, invited speaker or guest lecturer presentation, etc.) to ViiV Healthcare /and/or designee at least 30 days before they are submitted for publication or otherwise disclosed. If any patent action is required to protect intellectual property rights, Investigator agrees to delay the disclosure for a period not to exceed an additional 60 days.

Investigator will, on request, remove any previously undisclosed Confidential Information (other than the Study results themselves) before disclosure.

If the Study is part of a multi-centre study, Investigator agrees that the first publication is to be a joint publication covering all centers. However, if a joint manuscript has not been submitted for publication within 12 months of completion or termination of the Study at all participating sites, Investigator is free to publish separately, subject to the other requirements of this Section.

For all publications relating to the Study, Institution will comply with recognized ethical standards concerning publications and authorship, including Section II - "Ethical Considerations in the Conduct and Reporting of Research" of the Uniform Requirements for

Manuscripts Submitted to Biomedical Journals, <http://www.icmje.org/index.html#authorship>, established by the International Committee of Medical Journal Editors.

Publication of study results is also provided for in the Clinical Study Agreement between Pfizer and the Institution. In this section entitled Publications by Investigators, the defined terms shall have the meanings given to them in the Clinical Study Agreement.

15. OVERSIGHT COMMITTEES

15.1. Scientific Steering Committee

The Scientific Steering Committee (SSC) is an external group of epidemiology, biostatistics, infectious disease/HIV medicine, hepatology, cardiology, and oncology experts that will serve two roles: (1) to safeguard the interests of study participants and (2) to monitor study conduct, in conjunction with the sponsor study team. The remit of the SSC will be described in the charter for the SSC. In summary, the role of the SSC will be to periodically monitor the progress of the study, including logistical and operational aspects, to establish acceptable performance criteria (eg, acceptable rates of withdrawn consent and loss to follow-up), to evaluate the quality of the data being collected in the study, and to assist the sponsor in the development of any remedial plans of action as necessary. The SSC may propose changes to the study design and conduct including follow-up duration, as the committee deems necessary based on emerging safety data. In the event of recommendations for a significant change by the SSC, the Sponsor will notify regulatory agencies where necessary, as per legal or regulatory requirements.

15.2. Endpoint Committee

The Endpoint Committee will review all study endpoints occurring over the course of the study. The EC will be comprised of an independent group of infectious disease specialists, hepatologists, cardiologists and oncologists experienced in the treatment of HIV-1 infection and/or the study of HIV in large observational study settings. The members of the EC will receive de-identified data gathered on subjects who are suspected to have experienced a study outcome and will be responsible for adjudicating and coding the endpoints as described in Section 7.4.

Appendix 2. Enrollment procedure

0901717e1928d33f51Approved/Approved On: 07-Jan-2020 12:23 (GMT)

Appendix 3. Calculation of person-time expected to be accrued in the study

Scenario 1

Endpoints: All cause mortality, Liver-related death, Malignancies, Myocardial ischemia and infarction

Expected person-time of observation in maraviroc exposed and unexposed groups:

These events occurring at anytime during the 5-year follow up period will be adjudicated and analyzed as study endpoints. It is assumed that each year 10% patients will be lost to follow-up and that on average these losses will occur at the midpoint of the 12 months period.

Person-time accrual in the maraviroc exposed and unexposed groups for all cause mortality, Liver-related death, Malignancies, Myocardial ischemia and infarction				
	n at the beginning of period	Lost to follow-up midway of the period (provide 6 months of follow-up)	n at the end of the period (provide 12 months of follow-up)	Person-Years accrued
Year 1	1500	150	1350	1425.0
Year 2	1350	135	1215	1282.5
Year 3	1215	122	1093	1154.0
Year 4	1094	109	984	1038.5
Year 5	984	98	886	935.0
			Total person-years	5835.0

Based on the above assumptions, both these groups will accrue 5835 person-years of follow-up during the study for the assessment of all cause mortality, Liver-related death, Malignancies, Myocardial ischemia and infarction.

Scenario 2:

Endpoints: CDC category C AIDS-defining opportunistic infection, viral encephalitis, liver failure, rhabdomyolysis

Expected person-time of observation in:

These events will be adjudicated and analyzed as study endpoints if they occur during use of maraviroc or the anchor drug in the OBT, or within 6 months following their discontinuation

- Based on clinical experience, it is assumed that the rate of drug discontinuation will be higher in the earlier part of the study and will gradually decrease over time. To obtain a conservative estimate, it is assumed based on the observations from the 48-week clinical development program of maraviroc that the rate of discontinuation will be approximately 30% during the first 6 months of therapy, 25% between the 7th and 12th month, 20% between the 13th and 18th months and 15% in each 6 month

090177e1928d33f51Approved/Approved On: 07-Jan-2020 12:23 (GMT)

period thereafter. For the purpose of this calculation it is assumed that on average discontinuation occurs at the midpoint of each 6-month period.

- It is assumed that 5% of the patients (either continuing maraviroc or during the 6 months post discontinuation follow-up) will be lost every 6 months and on average these losses will occur at the midpoint of the 6-month period.
- Patients lost to follow-up during any 6-month period (either on or off maraviroc) will contribute only 3 months of follow-up time during that period. Patients who are being actively followed up at the end of each 6-month period will contribute 6 months of follow-up time.

Based on the above assumptions, both these groups will accrue 2875 person-years of follow-up during the study for the assessment of AIDS-defining OI, viral encephalitis, rhabdomyolysis and liver failure.

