6.4. Patients lost to follow-up

A patient will be categorized as lost to follow-up if there has not been any contact with the patient for six months since last contact and attempts to reach the patient and/or his/her secondary contact person(s) fail.

In the situation where neither the patient nor the secondary contact person(s) can be reached, attempts will be made to ascertain the vital status of the patient by searching the appropriate national or regional vital status registry or other relevant databases, where available and allowable by local law. Depending on the local law, this search will be conducted by a designated CRO, or a professional search firm, or the enrolling physician or his/her designee at the study site. Medical records of these patients cannot be obtained or reviewed for adjudication of any death event. Therefore, the supplemental data on the un-adjudicated mortality events will not be included in the primary analyses of the study. It should be noted that there is usually a lag between calendar time of death and the time that data are available from vital status registries, due to the additional time necessary for government agencies to collate information from regional death registries and to check these data for accuracy. In the U.S. National Death Index, the delay is approximately 18 months.

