6.6. Termination of follow-up

Follow-up will terminate at the earliest of any of the following events:

- Withdrawal of consent by the patient;
- Death of the patient;
- Completion of five years since entry into the study;
- Switching to another CCR5 inhibitor medication (Applicable for maraviroc recipients);
- If a patient in the maraviroc-unexposed comparator group commences treatment with a CCR5 inhibitor other than maraviroc, study follow-up will terminate. If a patient in the maraviroc-unexposed comparator group commences treatment with maraviroc, the follow-up will continue as usual. However, the follow-up experience after commencement of maraviroc will be attributed to the maraviroc-exposed group;

090177e1928d33f51Approved Approved On: 07-Jan-2020 12:23 (GMT)

- Discontinuation of the study by the Sponsor.

This study may be terminated or suspended by the Sponsor at any time. If the study is terminated or suspended, the Sponsor will promptly inform the enrolling physicians/institutions and the regulatory authorities. The IRB/IEC will be promptly informed and provided the reason(s) for the termination or suspension by the enrolling physician/institution, as specified by applicable regulatory requirement(s).

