9.1. Sample Size

The sample size for the study was determined based on an extensive feasibility assessment in 28 countries, input from Pfizer country offices, and in consultation with the regulators. This number was estimated to be 3,000 subjects (1,500 patients receiving maraviroc and

1,500 patients not receiving maraviroc) to allow calculations of reliable and precise risk estimates.

Malignancies, myocardial ischemia or infarction and deaths (liver-related and all cause) occurring at any time during the 5-year follow-up period will be adjudicated and analyzed as study endpoints. Assuming up to 10% annual loss to follow-up, the 1,500 patients each receiving maraviroc or the anchor drug will contribute 5,836 person-years of observation for these study endpoints over a 5-year period (See Scenario 1 in [Appendix 3](#) for details) in each treatment arm. It is assumed that the expected incidence rates are 12.7 per 1000 person-years for malignancies,¹⁴ 3.5 per 1,000 person-years for myocardial infarction,¹³ 2.35 per 1,000 person-years for liver-related deaths,¹⁵ and 16 per 1,000 person-years for all cause mortality¹⁵ in the internal comparator group of patients not receiving maraviroc.

CDC category C AIDS-defining opportunistic infections, viral encephalitis, rhabdomyolysis and liver failure will be adjudicated and analyzed as study endpoints if they occur during the use of maraviroc or the anchor drug in the OBT arm or within 6 months following maraviroc or anchor drug discontinuation. Accounting for the expected rates of drug discontinuation in the two treatment arms over time and a 10% annual loss to follow-up, each study arm will accrue 2,875 person-years of observation for these study endpoints (See Scenario 2 in [Appendix 3](#) for details). It is assumed that the expected incidence rates are 3.5 per 1,000 person-years for liver failure,¹⁶ and 160 per 1,000 person-years for AIDS-defining opportunistic infections¹⁷ in the internal comparator group of patients not receiving maraviroc.

Based on these assumptions of equal person years of contribution in the maraviroc exposed and unexposed groups, using a two-tailed test with $\alpha=0.05$, and a power of 80%, the minimum detectable relative rates for various study end points are reported in Table 2.¹⁸

Table 2. Minimum detectable relative rates using a two sided test, $\alpha =0.05$, and a power of 80%

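### Appendix 3 removes losses to follow-up but not deaths, so planned person-years are about 3.7% too high and Table 2 slightly too favourable

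*Protocol*

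**What the plan says.** Protocol Section 9.1 plans 1,500 patients per arm and gives 5,836 person-years per arm for malignancies, myocardial infarction or ischemia, liver-related death and death from any cause. Appendix 3, Scenario 1 gives 5,835: "both these groups will accrue 5835 person-years of follow-up during the study for the assessment of all cause mortality". The stated assumption reads: "each year 10% patients will be lost to follow-up and that on average these losses will occur at the midpoint of the 12 months period". The table has no other exit column. Section 9.1 words the same assumption as a ceiling: "Assuming up to 10% annual loss to follow-up".

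Section 9.1 also assumes "16 per 1,000 person-years for all cause mortality" in the comparator group, and Table 2 lists 93 expected deaths there.

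Elsewhere the protocol keeps the two exits apart. Section 6.4 defines loss as a failure of contact: "A patient will be categorized as lost to follow-up if there has not been any contact with the patient for six months". Section 6.6 opens with "Follow-up will terminate at the earliest of any of the following events" and lists death as an event of its own.

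Scenario 2 (2,875 person-years, for opportunistic infection, viral encephalitis, liver failure and rhabdomyolysis) deducts drug discontinuation and 5% loss per six months. It mentions no deaths. SAP 4.2.1 and 9.3 repeat these calculations.

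**The concern.** The plan counts 93 deaths per comparator arm as events but leaves the same patients in the denominator until they are lost or reach five years. On the protocol's own definitions those deaths are not part of the 10%. The 5,835 and 2,875 person-years feed every expected count and detectable ratio in Table 2, and so the 80% power statement. The omission acts in one direction: expected counts come out too high and detectable ratios too low. In a post-approval safety study that means somewhat overstating the ability to detect harm.

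**Working it through.** **Inputs.** From Protocol 9.1 and Appendix 3: 1,500 per arm; 10% annual loss at mid-year; five years; comparator rates per 1,000 person-years of 16 (death), 12.7 (malignancy), 3.5 (myocardial infarction) and 2.35 (liver-related death); two-sided 0.05; 80% power; equal person-time. The SAP text as read shows 5 for infarction, possibly an extraction fault. The 20 events in Table 2 match 3.5.

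**Step 1: reproduce the plan.** 1,500 × 0.95 × (1 + 0.9 + 0.81 + 0.729 + 0.6561) = 5,835.5 person-years. So the stated figure contains loss to follow-up and nothing else. 5,835 × 0.016 = 93.4 deaths, which is Table 2's 93.

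**Step 2: reproduce the detectable ratios.** The documents cite a reference for the method but print no formula. The closest fit found is a conditional binomial comparison of two Poisson counts with a continuity correction. For ratio R, let p = R/(1+R) and d = p − 0.5. Then m = [(1.96 × 0.5 + 0.8416 × √(p(1−p)))/d]², total events N = (m/4)[1 + √(1 + 2/(m·d))]², and comparator events = N/(1+R). At R = 1.464: p = 0.594, m = 219.0, N = 229.5, comparator events 93.1.

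| Endpoint | Events in Table 2 | Printed ratio | Formula |
|---|---|---|---|
| Opportunistic infections | 460 | 1.1955 | 1.1955 |
| All-cause mortality | 93 | 1.464 | 1.464 |
| Myocardial infarction | 20 | 2.136 | 2.137 |
| Liver-related deaths | 14 | 2.410 | 2.418 |
| Liver failure | 10 | 2.760 | 2.757 |
| Malignancies | 74 | 1.572 (table), 1.527 (text) | 1.528 |

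The malignancy value in the text reproduces and the one in the table does not. By this formula 1.572 would correspond to about 64 events, not 74.

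**Step 3: remove deaths.** In each year, losses L = 0.10n, deaths D = 0.016 × person-years, and person-years = n − (L + D)/2. Hence D = 0.016(n − L/2)/1.008.

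| Year | n at start | Lost | Died | Person-years |
|---|---|---|---|---|
| 1 | 1,500 | 150.0 | 22.6 | 1,413.7 |
| 2 | 1,327.4 | 132.7 | 20.0 | 1,251.0 |
| 3 | 1,174.6 | 117.5 | 17.7 | 1,107.0 |
| 4 | 1,039.5 | 103.9 | 15.7 | 979.6 |
| 5 | 919.8 | 92.0 | 13.9 | 866.9 |

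The total is 5,618 person-years (−3.7%). A continuous-time version gives 5,623.

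**Step 4: carry forward** (before-and-after figures use unrounded events).

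| Endpoint | Events before → after | Detectable ratio before → after |
|---|---|---|
| All-cause mortality | 93.4 → 89.9 | 1.464 (printed) → 1.473 |
| Malignancies | 74.1 → 71.4 | 1.527 (text) → 1.539 |
| Myocardial infarction | 20.4 → 19.7 | 2.12 → 2.15 |
| Liver-related deaths | 13.7 → 13.2 | 2.44 → 2.47 |

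Power for all-cause mortality at 1.464 falls from 80.1% to 78.5% if both arms have 5,618 person-years. Under that alternative the exposed arm dies at 16 × 1.464 = 23.4 per 1,000 and accrues 5,521 person-years (−5.4%), with 129 deaths instead of 137. Power is then 78.1%.

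**Step 5: Scenario 2.** The documents show no table for it, so this is approximate. A continuous-time rebuild from the stated discontinuation and loss rates gives 2,881 person-years (stated 2,875). With deaths at 16 per 1,000 it gives 2,812, a fall of 2.4%. Applied to the stated figure, 2,875 × 0.976 × 0.160 ≈ 449 opportunistic infections instead of 460.

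**The case against.** The strongest reply is that Section 9.1 gives 10% as an upper bound. About 8.5% annual loss plus deaths at 16 per 1,000 still yields 5,835 person-years, so the figure is attainable within the stated ceiling. That is true. It rules out saying that the design cannot deliver 5,835. However, Appendix 3 applies the full 10% as loss alone, and neither document says that the 10% includes deaths.

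The second reply is that the effect is trivial and the power loss depends on a formula inferred from Table 2. Without the continuity correction, mortality power at 1.464 with 89.9 events is about 80.5%. The planned analysis is a Poisson model adjusted for propensity quintile, not this test. The sample size rested on feasibility and consultation with regulators, SAP 4.1 states no hypotheses, and the final rates will use observed person-time. All of this stands and limits the point to a restatement of planning figures.

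A reader might also infer that consent withdrawals and transfers to other physicians lower the person-years much further. The documents do not support a figure. They give no rate for either exit and do not say whether the 10% includes them. SAP 4.2.2 continues follow-up of transferred patients for mortality, although Protocol 6.5 discontinues them.

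Nor does power fall below 80% at every printed ratio. At the 1.572 that Table 2 prints for malignancies, power with deaths removed is about 84%.

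**Conclusion.** The omission is real and small. It is an exit left out of the calculation; the table's own sums are right. At the full 10% loss, comparator person-years are about 5,620 rather than 5,835/5,836. The detectable mortality ratio is about 1.473 rather than 1.464, and power at the stated ratio is lower by roughly two percentage points or less. This rests on a constant death rate of 16 per 1,000, deaths at mid-year on average, the 10% excluding deaths as Sections 6.4 and 6.6 imply, and the inferred continuity-corrected formula. The Scenario 2 figure is less certain because its table is not shown. It would be wrong to conclude that the study is underpowered in any material way: no extra patients are needed and no conclusion of the study depends on these figures.

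**What to change.** Choose one of two routes.

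- Add a death column, at the assumed 16 per 1,000 person-years, to both Appendix 3 calculations. Then restate the person-years, expected events and detectable ratios in Protocol 9.1 and Appendix 3 and in SAP 4.2.1 and 9.3. For Scenario 1 that means about 5,620 person-years, 90 deaths, 71 malignancies, 19.7 infarctions and 13.2 liver-related deaths.
- If the 10% is meant to cover all exits including death, say so in the same places and keep the figures.

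Under either route, settle on one person-years figure (5,835 or 5,836) and reconcile the malignancy ratio between Table 2 and the text below it. The cost is a short recalculation and some wording. The only downside of the first route is slightly larger detectable ratios.
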